1.1 Scope

This document is a supplement to the BACE-N protocol (ClinicalTrials.gov Identifier: NCT04261309) and comprises a SAP for the article “Healthcare utilization and related cost among older people seeking primary care due to back pain: a prospective cohort study with one year of follow up”. The current SAP has been written while data collection was ongoing (we had access to baseline data, but not to follow-up data) and it will be uploaded to the ClinicalTrials.gov before full access to the study database.

2. Administrative information

Version of SAP

1.0

Study sponsor

Oslo Metropolitan University, the Norwegian Fund for Post-Graduate Training in Physiotherapy and “Et liv i bevegelse” (A life in movement) - Norwegian chiropractors’ research foundation

Names, affiliations and roles of SAP contributors

Name	Title	Affiliation	Role
[name]	[name] University [name] [contact] Email: [contact]	Principal Investigator
[name]	PhD-student	Oslo Metropolitan University	Main author of SAP
[name]	[name] University	Contributor to SAP
[name]	[name]	Contributor to SAP
[name]	[name] University	Statistical advisor
[name]	PhD-student	Oslo Metropolitan University	Contributor to SAP
[name]	PhD-student	Oslo Metropolitan University	Contributor to SAP

Signatures: person writing SAP, senior statistician and principal investigator

[name]

Main author of the SAP

[name]

Senior statistician responsible

[name]

Principal Investigator

3. Study aim

The primary aim of this study is to describe healthcare utilization and estimate associated costs during one year of follow up of older people seeking primary care due to a new episode of back pain. The secondary aim is to describe frequency of healthcare utilization across patients with different risk profile stratified according to the StarT Back Screening tool.

4. Study design, population and method

Study design

A prospective observational cohort study with one year of follow-up within a Norwegian primary care setting.

Study population and recruitment

Eligible patients are people 55 years of age or older who seek primary care (physiotherapist, chiropractor or GP) with a new episode of back pain (preceded by 6 months without visiting a primary care provider for similar complaints). Patients are excluded if they have difficulties completing the questionnaires (e.g. unable to speak, read or write in Norwegian) or if they have difficulties completing the physical examination (e.g. are wheelchair bound).

Patients were recruited from physiotherapists, chiropractors and GPs working in Norwegian primary care between April 2015 and February 2020. Patients who met the eligibility criteria and completed the consent to participate were included in the study.

Method

At baseline all patients completed a comprehensive questionnaire and underwent a standardized physical examination conducted by local research assistants at test stations established within each recruiting area. Follow-up questionnaires will be sent at 3, 6, and 12 months after inclusion for completion at home. All questionnaires are preferably completed electronically using the Infopad system, but paper versions will be available for patients not familiar with electronic data collection. All information will be stored and analysed securely through Service for sensitive data (TSD) at the University of Oslo, Norway.

Variables

Outcome variables

The primary outcome of this study is total costs of healthcare utilization (summed up for one year of follow-up). The secondary outcome is frequency of healthcare utilization (summed up for one-year of follow-up across patients with different risk profile according to the StarT Back Screening tool).

Healthcare utilization will be self-reported, collected through follow-up questionnaires, and include; consultation to healthcare professionals (type and frequency), number of diagnostic examinations (type and frequency), number of days of hospitalization and/or institutionalisation, back operations and use of back medication (both prescription and over-the-counter, type and frequency). All variables, except the “operation” variable, will be

reported with a 3 month recall period at 3, 6, and 12 months follow-up. The “operation” variable will be reported with a 12 month recall period at 12 months follow-up. Healthcare utilization during the one year of follow-up will be described as shown in table 3 and table 5. The total cost of healthcare utilization will be estimated based on information presented in table 3 and unit costs of healthcare resources collected from national pricelists (see table 1).

Screening tool

The Keele StarT Back Screening Tool (SBST) [1] will be used to classify the included patients into low, medium or high risk of poor disability outcome. The SBST is a brief 9-item tool designed to screen primary care patients with low back pain for prognostic indicators that are relevant to initial decision making. The tool is summed to produce an overall score from zero to nine and a psychological subscale score from zero to five. Patients with an overall score between 0-3 are classified as low risk. Patients with an overall score of minimum 4 and a subscale score of maximum 3 are classified as medium risk. Patient with an overall score of minimum 4 and a subscale score of 4 or 5 are classified as high risk. The SBST was translated into Norwegian by [name] and [name] in 2012, and has shown to have an acceptable accuracy in distinguishing between low back pain patients who have recovered or not after 1 year of follow-up [2].

Other variables

Included patients will be described with respect to the following baseline characteristics: age, gender, ethnicity, educational level, first healthcare provider, pain location, pain severity, pain duration, pain history, disability, comorbidity, health-related quality of life, emotional well-being, kinesiophobia and healthcare utilization six weeks prior to inclusion (table 2).

The Numeric Rating Scale (NRS) will be used to measure average pain severity last week [3]. The NRS, scored from 0 (no pain) to 10 (maximum pain), has been widely used to evaluate pain and has proven to be preferable when examining low back pain patients [4], also for Norwegian patients [5].

The Roland Morris Disability Questionnaire (RMDQ) [6] will be used to measure disability. The RMDQ is a widely used back-specific patient-reported measure of pain-related disability (0 = no disability, 24 = totally disabled). The Norwegian version has been validated and found to have good measurement properties when used among patients with low back pain [5, 7].

The Self-Administered Comorbidity Questionnaire (SCQ) [8] will be used to assess comorbidity. The SCQ is a 14-item measure of comorbidity for clinical and health services research settings. An individual can receive a maximum of 3 points for each medical condition: 1 point for the presence of the problem, another point if he/she receives treatment for it, and an additional point if the problem causes a limitation in functioning. Because there are 12 defined medical problems and 3 optional conditions, the maximum score totals 45 points if the open-ended items are used and 36 points if only the close-ended items are used.

The Short Form-36 Health Status Questionnaire (SF36) [9] will be used to assess health-related quality of life. The SF36 consist of 36 items. It measures health on eight multi-item

dimensions, covering physical functioning, social functioning, role limitations (physical problems), role limitations (emotional problems), mental health, vitality, pain, and overall evaluation of health [9]. Data-completeness of the SF36 in the general population in Norway seems to strongly declined with increasing age [10]. Hence, caution should be exercised when assessing subjective health or employing the norms among subjects aged 70 years or over [10].

The Center for Epidemiologic Studies Depression Scale (CES-D) will be used to assess emotional well-being. The CES-D has been widely used in studies of late-life depression. Psychometric properties are generally favourable [11]. The Norwegian version of the CES-D has been used among older patients in order to measure depression symptoms [12].

The Fear Avoidance Beliefs Questionnaire, physical activity subscale (FABQ-PA) [13] will be used to assess kinesiophobia. The FABQ-PA consists of four questions aimed towards physical activity, scored on a 7-point ordinal scale, which are summed up to a sum score, ranging from 0 (no fear) to 24 (maximum fear). The questionnaire has been translated into Norwegian and has shown acceptable psychometric properties in Norwegian patients with low back pain [14].

5. Statistical analyses

General analysis considerations

All analyses described in this plan are considered a priori in that they have been defined in the protocol and/or in this SAP. All post hoc analyses will be identified as such in the article if relevant. All analyses will be carried out by a PhD-student using SPSS version 26 and controlled by a senior researcher/statistician. All statistical tests will be two-sided, and nominal p-values will be reported. Preliminary analyses assessing the influence of missing data and assumptions of normality for continuous variables will be conducted. The assumption of normal distribution will be investigated using histograms and QQ-plots. Normally distributed data will be presented with means and standard deviations (SDs), skewed data with medians and interquartile range (IQR). Categorical data will be reported as counts and percentages. Missing data will be handled by multiple imputation, using 5 imputations and 10 iterations unless the missingness exceeds 30% and/or missing at random cannot be assumed. Fully conditioned specification method and regression estimation will be used. For variables where we are unable to use regression estimation due to computational difficulties, predictive mean matching will be used [15].

Description of study flow

The flow of participants through the study will be reported according to the STROBE guidelines [16] with a flow chart (see figure 1). Reasons for dropout will be provided where known. Differences between responders and non-responders will be evaluated.

Participant characteristics

Baseline characteristics of included patients will be presented for the whole sample and the following subgroups: (1) low, (2) medium, and (3) high risk of persistent disabling back pain according to the StarT Back Screening tool (see table 2).

Primary analysis

First, type and frequency of different healthcare resources will be calculated for each of the follow-up periods; from baseline to 3 months, 3 to 6 months, and 9 to 12 months and presented as shown in table 3.

Next, costs will be estimated based on information presented in table 3 and unit costs of healthcare resources collected from national pricelists (see table 1). Costs related to back medication will be estimated based on medication type (not exact medication name) and frequency of use. Data on dosage is not available. All costs will be presented in Norwegian Krones (NOK) and euros (€) 2020. Costs of healthcare utilization will be described with median and interquartile range for each follow-up period and for the whole year as shown in table 4. If data is highly skewed, bias-corrected and accelerated bootstrapping will be considered to derive confidence intervals for cost estimates.

Secondary analysis

First, type and frequency of different healthcare resources will be described for the one-year of follow-up for the following subgroups: (1) low, (2) medium, and (3) high risk of persistent disabling back pain according to the StarT Back Screening tool and presented as shown in table 5.

Next, Kruskall Wallis test will be used to determine whether there is a significant difference between the three subgroups with regards to; number of primary care consultations, number of patients using back medication, number of patients receiving imaging (X-ray, MRI, CT) and number of patients receiving secondary care (back operation, hospitalization, rehabilitation stay). For all analyses, p values of < 0.05 will be considered statistically significant.

Sample size and statistical power consideration

This study contains secondary analyses embedded in the BACE-N study. Details on sample size calculation are provided in the BACE-N protocol (ClinicalTrials.gov Identifier: NCT04261309). With a sample size of 450 participants within the BACE-N study, we assume to have expectable power to describe healthcare utilization and estimate associated costs [17].

Sensitivity analyses

To assess the robustness of the results, the following sensitivity analyses will be carried out for cost calculations related to the primary analysis:

1. Complete case analysis (without using imputation for missing data)
2. Without outliers (outliers will be identified with simple scatter plots by visual inspection)

6. Selection bias, information bias and confounding

Selection bias:

Because of limited resources and practical reasons related to recruitment from a broad network of clinicians, the BACE-N lacks information on eligible study participants that declined to participate or for other reasons were not invited. Therefore, in order to assess representativeness, the BACE-N study sample will be compared on key sociodemographic variables with a sample from the longitudinal population study of people in the second half of life; The Norwegian study on life course, ageing and generation (NORLAG) [18]. The NORLAG study is expected to represent a representative sample of older people with musculoskeletal complaints.

Response rate at each assessment point and reasons for loss to follow-up will be reported. Key baseline characteristics will be compared between those lost to follow-up and those remaining in the study.

Information bias:

To reduce the risk of information bias, the study outcome (costs) will be measured in an identical manner in all included cases, and in the best possible way within the framework of the BACE-N study.

Covariates:

Covariates may influence estimates of our primary outcome. Therefore, in line with the PROGRESS framework and recommendations for type 1 studies [19], we will describe potential covariates and the way they may alter our primary outcome.

Potential covariates of costs related to healthcare utilization: gender [20-25], age [20, 22, 26], educational level [27, 28], pain duration [21, 28-30], pain history [25], pain severity [22, 25, 30, 31], radiating pain below the knee [29], disability [21, 23, 25, 28, 29], comorbidity [26, 32, 33], health-related quality of life [23], emotional well-being [21, 28, 29, 31, 32], kinesiophobia [29, 34], first healthcare provider [35] and costs related to healthcare utilization prior to inclusion.

Table 1 Cost categories, units, unit price, all numbers in Euros (€) and Norwegian kroner (NOK) for 2020

Cost categories	Unit	Unit price (€)	Unit price (NOK)	Reference (source)
Primary care				
General practitioner	Per visit			
Physiotherapist	Per visit			
Chiropractor	Per visit			
Manuel therapist	Per visit			
Naprapath	Per visit			
Osteopath	Per visit			
Psychologist	Per visit			
Other therapists	Per visit			
Back medication				
Paracetamol	Per daily defined dose			
NSAID	Per daily defined dose			
Muscle relaxant	Per daily defined dose			
Sleep medication	Per daily defined dose			
Cortisone	Per daily defined dose			
Opioid	Per daily defined dose			
Others	Per daily defined dose			
Examinations				
Blood sample	Per examination			
X-ray	Per examination			
MRI	Per examination			
CT	Per examination			
Others??	Per examination			
Secondary care				
Back operation	Per operation			
Hospitalization (non-operation)	Per day			
Rehabilitation stay	Per day			

NoMA, Norwegian Medicines Agency

Table 2 Patient characteristics and clinical status at baseline (n = X)

	All participants (n = x)	Stratified risk profile*		
		Low (n = x)	Medium (n = x)	High (n = x)
Male, N (%)				
Age in years, mean (SD)				
Educational level high, N (%)				
Ethnicity Norwegian, N (%)				
First healthcare provider, N (%)				
General practitioner				
Physiotherapist				
Chiropractor				
Pain location, N (%)				
Lumbar				
Thoracic				
Radiating pain below the knee				
Pain severity last week (NRS 0-10), median (IQR)				
Pain duration, N (%)				
< 6 weeks				
6 weeks to 3 months				
> 3 months				
Previous episodes of back pain, N (%)				
Disability (RMDQ 0-24), mean (SD)				
Comorbidity (SCQ, 0-15)				
Health-related QOL (SF36, 0-100), mean (SD)				
Physical component				
Mental component				
Emotional well-being (CES-D 0-60)				
Kinesiophobia (FABQ-PA 0-24)				
Healthcare utilization prior to inclusion				
Patients with primary care consultation last 6 weeks, N (%)				
General practitioner				
Physiotherapist				
Chiropractor				
Manual therapist				
Naprapath				
Osteopath				
Psychologist				
Other therapists				
Patients with use of back medication, N (%)?				
Patients with additional diagnostic examination last 6 months, N (%)				
Blood sample				
X-ray				
MRI				
CT				
Patients with previous hospitalization, N (%)				
Patients with previous rehabilitation stay, N (%)				

* According to the StarT Back Screening Tool

Table 3 Healthcare utilization throughout one-year of follow-up

	0-3 months	>3-6 months	>9-12 months
Primary care			
Patients with primary care consultation, N (%)			
General practitioner			
Physiotherapist			
Chiropractor			
Manual therapist			
Naprapath			
Osteopath			
Psychologist			
Other therapists			
Number of general practitioner consultations, median (IQR)			
Number of physiotherapist consultations, median (IQR)			
Number of chiropractor consultations, median (IQR)			
Number of manual therapist consultations, median (IQR)			
Number of naprapath consultations, median (IQR)			
Number of psychologist consultations, median (IQR)			
Number of other consultations, median (IQR)			
Back medication			
Patients with use of back medication, N (%)			
Paracetamol			
NSAID			
Muscle relaxants			
Sleep medication			
Cortisone			
Opioid			
Others			
Frequency of use paracetamol, N (%)			
Daily			
Weekly			
Monthly or less			
Frequency of use NSAID, cortisone N (%)			
Daily			
Weekly			
Monthly or less			
Frequency of use muscle relaxants, sleep medication, N (%)			
Daily			
Weekly			
Monthly or less			
Examinations			
Patients with additional diagnostic examination, N (%)			
Blood sample			
X-ray			
MRI			
CT			
Secondary care			
Patients with back operation, N (%)			
Patients with hospitalization, N (%)			
Duration of stay in days, median (IQR)			
Patients with rehabilitation stay, N (%)			
Duration of stay in days, median (IQR)			

Table 4 Cost due to healthcare utilization from 0-3 month, >3-6 months, >9-12 months and the entire follow-up period (0-12 month)

	0-3 months	3-6 months	>9-12 months	0-12 months*
Primary care				
General practitioner				
Physiotherapist				
Chiropractor				
Manual therapist				
Naprapath				
Osteopath				
Psychologist				
Other therapists				
Back medication				
Paracetamol				
NSAID, cortisone				
Muscle relaxants, sleep medication				
Examinations				
Blood sample				
X-ray				
MRI				
CT				
Secondary care				
Back operation				
Hospitalization and/or rehabilitation stay				
Total costs				

Values are median (interquartile range) of costs (€). *Cost due to healthcare utilization for the entire follow-up period is calculated on the basis for the three follow-up periods

Table 5 Healthcare utilization throughout one-year of follow-up, across patients with different risk profile according to the StarT Back Screening tool

	Stratified risk profile		
	Low (n = x)	Medium (n = x)	High (n = x)
Primary care			
Patients with primary care consultation, N (%)			
Number of primary consultations, median (IQR)			
Back medication			
Patients with use of back medication, N (%)			
Paracetamol			
NSAID			
Muscle relaxants			
Sleep medication			
Cortisone			
Opioid			
Examinations			
Patients with additional diagnostic examination, N (%)			
Blood sample			
X-ray			
MRI			
CT			
Secondary care			
Patients with back operation, N (%)			
Patients with hospitalization, N (%)			
Patients with rehabilitation stay, N (%)			

[figure not shown]

Figure 1. Flow chart of the study

References

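### SAP 1: skew and excess zeros do not trigger predictive mean matching, so normal-regression imputation could bias the median three-window cost upward; its 30% rule also differs from SAP 2's

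*Combined protocol and SAP*

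**What the plan says.** SAP 1 is the plan for the utilization and cost article; SAP 2 is the plan for modifiable prognostic factors of high cost.

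- **Imputation model** (SAP 1, section 5, General analysis considerations): "Fully conditioned specification method and regression estimation will be used". The exception is "For variables where we are unable to use regression estimation due to computational difficulties, predictive mean matching will be used".
- **When imputation applies** (same section): "using 5 imputations and 10 iterations unless the missingness exceeds 30% and/or missing at random cannot be assumed".
- **Checks** (same section): "Preliminary analyses assessing the influence of missing data and assumptions of normality for continuous variables will be conducted". The stated use of the normality check is to choose between mean and median summaries.
- **Outcome** (Primary analysis): "Costs of healthcare utilization will be described with median and interquartile range for each follow-up period and for the whole year". Skew is expected: "If data is highly skewed, bias-corrected and accelerated bootstrapping will be considered to derive confidence intervals for cost estimates".
- **One-year total** (Table 4 footnote): "Cost due to healthcare utilization for the entire follow-up period is calculated on the basis for the three follow-up periods".
- **Sensitivity analysis bearing on imputation**: "Complete case analysis (without using imputation for missing data"). No alternative imputation model is listed.

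SAP 2 (section 5, General analysis considerations) has the same imputation text, except that its exception requires more than 30% missing *and* failure of missing at random (MAR). Its outcome is the same BACE-N one-year cost, split at the top quarter.

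**The concern.** A linear regression computes without trouble on skewed data with many zeros. The condition that brings in matching would therefore not be met by the variables that need it most. Normal draws centre on the conditional mean, which under right skew lies above the median. They also produce negative values and almost no exact zeros. A bootstrap interval does not repair wrong imputed values, and nothing links the normality check to the imputation model.

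At stake is the primary outcome of SAP 1. One missed questionnaire leaves the total incomplete, so even moderate missingness per questionnaire affects many totals.

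The exception rule is a second, separate problem. The same cost data could be imputed in one article and not in the other. SAP 1 does not say whether 30% refers to one period or to the one-year total, and it does not say which analysis replaces imputation.

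**Working it through.** **Inputs.** The plan states no figure for the imputation or for cost, and the unit prices in SAP 1 Table 1 are blank. Distributions are therefore assumptions. The 15% missingness is borrowed from the dropout allowance in the SAP on disability and comorbidity: 450 × 0.85 = 382.5, stated there as about 380.

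**Direction, by hand.** Take one period with 30% zeros and log-normal users (median 1, log-SD 1.0).
- Mean = 0.7 × exp(0.5) = 1.154.
- Median = exp(Φ⁻¹((0.5 − 0.3)/0.7)) = exp(−0.566) = 0.568, so the mean is 1.154/0.568 = 2.03 times the median.
- SD = √(0.7 × exp(2) − 1.154²) = 1.960.
- Normal draws with this mean and SD are negative with probability Φ(−1.154/1.960) = 28%. They exceed the true median with probability Φ((1.154 − 0.568)/1.960) = 62%, where it should be 50%.

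**Size, by simulation.** n = 452, three periods summed, 5 imputations, 10 iterations, 200 replicates per setting. Missingness is completely at random, or at random given two observed baseline covariates in either direction, and overlaps between periods. The table shows the error in the median against the same three-window total with complete data, at 15% missing per questionnaire.

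| Assumed data (zeros by period; log-SD) | Normal regression |
|---|---|
| Mild (5/10/15%; 0.7) | +1 to +2% |
| Moderate (20/30/40%; 1.0) | +4 to +8% |
| Heavy (30/45/55%; 1.3) | +9 to +24% |
| Visit counts (20/30/40% zeros) | +1 to +2% |

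Matching gave −1 to +3% and two-part imputation was within 1%. Separately coded repeats moved the upper ends to about +9% (moderate), +26% (heavy) and +4% (matching). Setting negative draws to zero raised the regression error further, up to +38%.

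A differently built simulation, with rare large secondary-care costs added, gave +3 to +28% at 15% missing for zero shares of 20 to 70%. Regression was too high in all 22 scenarios completed.

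**Quartiles at 15% missing.** Upper: regression +1 to +15%, matching −1 to 0%. Lower: regression −14 to +4%, matching 0 to +21%, two-part −1 to +6%.

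**Complete case at 15% missing.** Error in the median: 0 to +1% if missing completely at random, −10 to −26% if higher-need patients drop out more, +10 to +34% if they drop out less. A gap between this analysis and the imputed one would not show which is wrong.

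**Exception rule.**

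| Missingness | MAR | SAP 1 read as *or* | SAP 2 |
|---|---|---|---|
| ≤30% | assumed | impute | impute |
| ≤30% | not assumed | do not | impute |
| >30% | assumed | do not | impute |
| >30% | not assumed | do not | do not |

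The rules disagree in two of four cases. The unit also matters: with 15% missing per questionnaire, the share of incomplete totals runs from 15% (same patients each time) to 1 − 0.85³ = 39% (independent). It was 26 to 29% in the main simulation.

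**The case against.** **The model is inferred.** The word linear, the imputed level, transformations and bounds are all unstated, and the yes/no and frequency-category items are not at issue. This stands. The bias claim is conditional; what is certain is that the plan names no safeguard for skew or zeros.

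**The size may be trivial.** It is +1 to +2% for mild data and for visit counts, and counts are a natural level at which to impute. This stands too. The larger errors need heavy zeros and skew, which the documents neither show nor exclude.

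**Matching has its own fault.** In zero-heavy data it can leave the lower quartile too high. That is correct, and it is why the fix specifies two-part imputation for those variables.

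**Complete-case analysis is already planned.** It could serve as the fallback, but SAP 1 does not name it as such, and it can itself be biased under MAR.

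Three stronger readings are tempting but unsupported.

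- *The reported cost will exceed the true 12-month cost.* Months 6 to 9 are not collected. In one assumed pattern the three-window median was 550 against 750 for four windows (550/750 − 1 = −27%), so the net error could have either sign.
- *The 30% limit is known to be crossed.* The latent-class SAP (Sample size) counts 306, 293 and 281 of 452 complete for its pain analysis, that is 32%, 35% and 38% incomplete. But only 358 were complete at baseline (94/452 = 20.8% already incomplete), and for other variables. Relative to 358 the shortfall is 14.5%, 18.2% and 21.5%. These counts do not show that cost items exceed 30% per questionnaire.
- *SAP 2's odds ratios are biased.* Nothing here shows that.

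**Conclusion.** The point holds in conditional form. As written, SAP 1 has no trigger that moves skewed or zero-heavy variables away from regression imputation. If those variables are imputed by normal linear regression, the median of the three-window total is too high relative to the complete-data three-window total. At 15% missing per questionnaire the error is about +1 to +2%, +4 to +9% or +9 to +26% for mild, moderate or heavy zeros and skew, against about −1 to +4% with matching. The direction was the same in every setting tried; the size rests on assumed distributions and missingness.

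The difference between the exception rules of SAP 1 and SAP 2 is a plain textual conflict and needs no assumption. Whether it will matter in practice cannot be told from the documents.

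The plan should be changed, because the outcome is primary and the better method is already named in it. Confidence is medium.

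**What to change.** In SAP 1:

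1. Name the imputed level and the model for each variable type. Impute counts, days and costs at item or period level before summing, by predictive mean matching instead of normal regression.
2. For zero-heavy variables, specify two-part imputation: any use first, then matching among users.
3. Compute the total, median and quartiles within each imputed data set.
4. Use one exception rule in SAPs 1 and 2. State the missingness limit and the MAR condition as separate conditions, and say whether 30% refers to a period or to the one-year total. Simply replacing *and/or* by *and* would not do: it would let MAR-based imputation proceed at up to 30% missing when MAR is judged untenable.
5. Name the fallback when imputation is not done: the planned complete-case analysis with its limits stated, or another analysis.
6. Keep complete case as a sensitivity analysis, and use the same imputed BACE-N costs in SAP 2.

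The cost is SAP wording and a little more programming and computing time. No new data are needed.

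### The cost SAP's primary outcome is total one-year cost, but only median and interquartile range are planned, so mean total cost per patient cannot be obtained from its tables; where data are imputed, regression without stated bounds is the default

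*Combined protocol and SAP*

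**What the plan says.** The first SAP in the combined document (the cost SAP below) states in section 4: "The primary outcome of this study is total costs of healthcare utilization". In section 5, Primary analysis, "Costs of healthcare utilization will be described with median and interquartile range for each follow-up period and for the whole year". The Table 4 footnote agrees: "Values are median (interquartile range) of costs". There is no mean column, and the total row is treated like the rest. For highly skewed data, "bias-corrected and accelerated bootstrapping will be considered to derive confidence intervals for cost estimates"; neither the statistic nor a commitment is given. The two cost sensitivity analyses (complete case, and outliers removed by eye) add no mean.

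On the annual column, Table 4 notes: "Cost due to healthcare utilization for the entire follow-up period is calculated on the basis for the three follow-up periods". These are months 0-3, 3-6 and 9-12. Only the operation "variable will be reported with a 12 month recall period at 12 months follow-up".

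On missing data, section 5 (General analysis considerations) plans five imputations by chained equations, "unless the missingness exceeds 30% and/or missing at random cannot be assumed". Regression is the default and no bound or transformation is stated. Predictive mean matching is kept for variables where regression cannot be computed. The second SAP, on modifiable prognostic factors of high cost, has the same default.

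**The concern.** A median describes a typical patient and is worth reporting. It does not determine the mean, and medians do not add across rows. Cost data usually have many zeros and a long right tail, so the two can differ several-fold. A study whose stated purpose includes estimating costs would then publish no average cost per patient. A mean computed later would fall under the SAP's own rule that unplanned analyses be identified as post hoc.

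The imputation issue is separate. Visit counts, days and costs cannot be negative. A normal linear model fits them without any computational failure, so the fallback would not be triggered, and nothing in the plan links the normality checks to the choice of imputation method. The model can give patients negative annual costs and move the quartiles, which are the only cost summaries planned.

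**Working it through.** **Inputs.** N = 450 comes from the cost SAP's sample size paragraph. The unit-price cells of Table 1 are empty, and no cost SD, precision target or cost missingness is stated. There is no planned cost figure to reproduce. Every price, user share, spread and missingness rate below is an assumption.

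**1. Do the quartiles fix the mean?** I drew 450 lognormal costs (median 500, log-SD 1.0) and raised only the top of the distribution. The sample quartiles stayed at 255 / 482 / 891 throughout.

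| Change | Total | Mean = total / 450 |
|---|---|---|
| none | 328,015 | 729 |
| top 9 raised to at least 10,000 | 368,969 | 820 |
| top 9 raised to at least 20,000 | 457,869 | 1,017 |
| top 22 raised to at least 20,000 | 682,202 | 1,516 |

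For a lognormal cost, mean / median = exp(s²/2). This is exp(0.32) = 1.38, exp(0.5) = 1.65, exp(1.125) = 3.08 and exp(2) = 7.39 for s = 0.8, 1.0, 1.5 and 2.0.

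**2. What can be rebuilt from Tables 1, 3 and 4?**
- Operations: users × unit price / N gives the mean if each user has one operation. For example, 9 × 10,000 / 450 = 200 per patient.
- X-ray, MRI, CT, blood sample: the same product is a lower bound, because Table 3 counts patients, not examinations.
- Consultations, hospital and rehabilitation days: Table 3 gives users and a median (IQR) number. The mean number is not available, so neither is the mean cost.
- Medication: frequency classes are tabulated, but no conversion from frequency to doses is given.
- Total: not available, because several of its components are not.

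**3. Denominator.** Table 4 does not say whether rows cover all patients or users only.
- All patients: the 75th percentile is 0 if at most about 112 of 450 use the item. The binomial probability is above 99% at 20% users and 94% at 22%. The row then prints 0 (0-0).
- Users only: users × median understates a lognormal total by 1 − exp(−s²/2), which is 27% at s = 0.8 and 45% at s = 1.1.

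**4. Regression imputation.** An unbounded normal model gives a negative draw with probability Φ(−1/CV): 16%, 25% and 31% for CV = 1, 1.5 and 2. Simulations at N = 450:
- Skewed visit costs, 15% / 30% missing in the last period: about 29% of imputed values negative, 2-4% of patients with a negative annual total, and the median +4% / +8%. Predictive mean matching moved the median under 1%.
- A wider set of visit-cost settings, same missingness, no inpatient days: median +3 to +15% / +7 to +31%, 75th percentile +1 to +5% / +2 to +11%, mean within 0.3%.
- With rare inpatient days added: median +5 to +12% / +14 to +33%, 75th percentile +19 to +30% / +39 to +59%.
- A single lognormal cost, 20% missing, s = 1.0 / 1.5: median 500 to 535 / 557, 75th percentile 978 to 1,096 / 1,374 to 1,807, mean unchanged (820 / 1,542).

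For scale, the 95% sampling half-width at N = 450 in the multi-setting simulations was 15-32% for the median and 15-25% for the 75th percentile. Predictive mean matching on resource use kept the median within +8% and the 75th percentile within about 2%. Applied to cost directly, with inpatient days, it moved the median by +4 to +26%.

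**5. Interval for the mean total.** With resource-level predictive mean matching, 25% missing and 200 datasets, Rubin-pooled intervals covered 95.0% without and 93.5% with inpatient days. Intervals from a single imputed set covered 93.5% and 89.5%.

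**6. Top-25% outcome in the second SAP.** Regression misclassified 0-5 more of 450 patients than predictive mean matching without inpatient days. It misclassified 29-42 more only when rare inpatient days were themselves imputed by regression.

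**The case against.** Median and interquartile range follow the SAP's own rule for skewed data, and the aim is descriptive. The optional bootstrap could be applied to a mean, and the patient-level data will always yield one. This is fair, but none of it puts a mean in the plan.

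Three stronger readings are tempting, and the documents do not support them.
- That no mean can be recovered for any row, so that a 0 (0-0) cell hides a costly item. Tables 1 and 3 would print its unit price and user count, and for operations these give an approximation.
- That the mean would multiply up to annual spending. Months 6-9 are unobserved except for operations, and section 6 of the cost SAP says there is no information on eligible people who declined or were not invited. Further assumptions would be needed.
- That the second SAP's high-cost classification is seriously distorted. In the simulations the effect is small unless rare inpatient days are imputed by regression.

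The imputation point is also conditional. The SAP for the 2-year clinical course reports 306, 293 and 281 complete at 3, 6 and 12 months for its pain analysis. That is 32-38% short of 452, which would switch imputation off in the cost SAP, or 15-22% short of the 358 complete at baseline, which would not. Neither figure is cost missingness. Bounded or transformed regression was not compared, so predictive mean matching is an adequate remedy, not the only one.

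**Conclusion.** The point holds in two separate parts. First, and from the documents alone: the primary outcome is total cost, only median and interquartile range are planned, and the planned tables do not yield mean total cost per patient or mean cost for multi-visit categories. In the illustrations the mean was 1.4 to 7.4 times the median, or doubled with no change in the planned output.

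Second, only where imputation is used: the regression default can produce negative annual costs and an upward shift in the median, with the mean hardly moved. The 75th percentile shifts less than the median for ordinary visit costs, and more under some assumptions, notably rare inpatient days. Direction was consistent across simulations; size was not, and all sizes rest on assumed prices, use and missingness. Both changes should be made; neither gap makes the planned medians wrong in themselves.

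**What to change.** 1. State that Table 4 covers all patients. Beside each median and interquartile range, report the arithmetic mean cost per patient. For total cost add a 95% interval: a bootstrap standard error within each imputed set pooled by Rubin's rules, and a bias-corrected and accelerated interval in the complete-case analysis. Label the annual column as the sum of three observed 3-month periods, with months 6-9 not observed except for operations.
2. Where imputation is used, make predictive mean matching the default for visit counts, days and costs, impute resource use before pricing it, and keep regression for roughly normal variables. The second SAP can adopt the same setting for consistency.

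The cost is 18 rows × 4 columns = 72 extra values, repeated in the second currency if both are tabulated, a mean total in each of the two sensitivity analyses, one pooling rule and one imputation setting. No new data are needed. The downside is that a mean is sensitive to extreme patients. The planned analysis without outliers can show how much, but should not replace the main result.
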